Clinical assessments include Auditory Hallucination Rating Scale (AHRS), the Psychotic Symptom Rating Scales (PSYRATS), the Scale for the Assessment of Positive Symptoms (SAPS), the Positive and Negative Symptoms Scale (PANSS) and the Cardiff Anomalous Perceptions Scale (CAPS). These clinical assessments involve answering questions about psychiatric symptoms. The total assessment time will take up to 1 hour 40 minutes. There will be baseline (week 0) and post-treatment (week 3) assessments. These assessments will be conducted by RAs who have completed training for each measure used. The Clinical Global Impression Scale (CGI-S and CGI-I) will be completed by [name] or other clinically trained personnel before each treatment session to quantify and track participant progress and treatment response over time, based on the above measures and general clinical impressions. AHRS assessment will be audiotaped. The second clinical rater will listen to an audiotaped session, blind to subject identity and session number. In addition, [name] or other clinically trained personnel will ask participants questions using the Systematic Assessment for Treatment of Emergent Events (SAFTEE), and this will be done once on each treatment day. The Columbia Suicide Severity Rating Scale (C-SSRS) will be conducted by a qualified clinician (e.g., physician, licensed clinical psychologist, psychiatric nurse practitioner, licensed clinical social worker, or other qualified mental health clinicians).

Participants will be administered the C-SSRS weekly to ensure that they meet the study safety/eligibility requirements. The study PI will be informed and will assess the participant for suicidality and safety. The PI will contact the participant's primary mental health provider to inform them of patient's current level of suicidality. If the PI determines that the participant is an immediate risk/danger to themselves or others, or feels that an emergency evaluation is clinically indicated, the patient will be referred the emergency room at CUMC/NYP-Columbia.

TMS Sessions:

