Transcranial Magnetic Stimulation (TMS) is a noninvasive tool for the study of the human brain that has been approved by the FDA for use in depression and is being investigated as a potential therapeutic agent in other areas of psychiatry and neurology. Contrary to single-pulse TMS, rTMS is able to change and modulate cortical activity that can last beyond the stimulation period, as a potential method for the treatment of neuropsychiatric conditions such as AVHs. We will deliver rTMS at a low frequency (1 Hz) to produce inhibitory effects that may be required to reduce the severity of AVHs. In our protocol, all participants will receive a 20-min once-daily rTMS sessions over a period of 2 weeks (weekends off), and therefore accrue a total of 10 rTMS stimulation sessions. The rTMS parameters that will be used are a frequency of 1 Hz (1 pulse per second) at an intensity of 90% of the motor threshold (MT). Therefore, we will deliver 1200 continuous pulses per session/day which adds up to 12,000 pulses in total for the whole treatment. These parameters are well within established safety guidelines. Although the goal is to deliver 10 sessions over 10 days of rTMS treatment, the treatment will still be considered complete if the participant misses at most two days of treatment over the two week period.

Localization of brain regions for stimulation

Localization of brain regions is done by establishing skull landmarks for each individual and matching these against an MRI of each participant's brain using Brainsight's camera/computer system for coregistration of each participant to his or her MRI. Each individual subject's structural MRI with overlay of the left TPJ target will be used to localize placement of the rTMS coil with frameless stereotaxy (Brainsight, Rouge Research, Inc., Montreal, Canada).

Criteria for Early Discontinuation

Subjects with a Clinical Global Impression-I (CGI-I) worsening of 2 or greater for two consecutive days, or a Clinical Global Impression-S (CGI-S) of 6 or 7 will trigger a clinical evaluation as to whether the patient should be discontinued. This will be documented in the clinical chart. Subjects who are unable to cooperate with study procedures (e.g., TMS, EEG, MRI) will be discontinued from the study.

Blood and other Biological Samples

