Urine samples will be collected for purposes of pregnancy testing. Approximately 30 mL will be collected, tested, and immediately discarded. Test results will be documented and kept on file under the subject number (no identifying information will be used in the documentation).

Clinical Treatment Alternatives

Standard-of-care treatment for persistent auditory hallucinations consists of use of antipsychotic medications. Cognitive behavioral therapy for voices is sometimes used as adjunctive treatment for coping with AVH.

Risks/Discomforts/Inconveniences

Risks Associated with COVID-19:

Going out in public and traveling involves some risk of infection with COVID-19. There is risk of COVID-19 infection during in-office visits and during travel for research purposes.

Risks Associated with Medical Screening:

Medical screening can be associated with minor psychological distress (answering emotionally difficult screening questions). Study personnel are trained at monitoring patient comfort and providing reassurance in the advent of psychological discomforts. Being informed of clinically significant findings may also cause psychological distress. [name] (PI), who is a licensed physician (NY State) and certified by ABPN in Psychiatry will discuss any such results with subjects to minimize distress and provide referral. [name] (collaborator), who is also licensed and board certified, will serve as a back-up in cases when [name] is unavailable.

Risks Associated with Clinical Assessments:

Distress can be experienced from thoughts or discussion about psychiatric symptoms. Some subjects may experience distress or anxiety related to participating in these procedures, and they will be encouraged to report any concerns. A psychiatrist will be available to assist the subject if needed, and subjects will be removed from the protocol if their distress of anxiety becomes intolerable. Also, each study participant will be provided with a 24-hour emergency contact number. Risks of an audiotaped AHRS assessment include boredom and fatigue, as well as risks to confidentiality and the protection of personal health and identifying information.

Risks Associated with TMS:

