there are no explicit risks to the subject by participating in EEG. The EEG recording is performed with the patient in an enclosed, sound-proofed room, which may cause mild anxiety, but they are monitored with a closed-circuit camera, told to wave at the camera if they need to get the technician's attention, and the door is frequently opened between task blocks to check in. In our experience, these measures have been sufficient to mitigate any initial anxiety about the recording room.

Risks Associated with MRI:

Some participants may experience sensations during the MRI scan, which are caused by changes in the magnetic field that can stimulate nerves in the body. Subjects will be instructed to report any tingling, muscle twitching, or painful sensations (very rarely) that might occur during scanning.

Some participants may find it uncomfortable to remain still and may experience minor distress by the confined and noisy conditions in the MRI scanner (i.e. claustrophobia) - they can come immediately out of the MRI scanner if this develops. Of note, both the FDA and the NYSPI IRB have deemed MRI Scanning on the GE 3Tesla MRI Scanner at the New York State Psychiatric Institute to be classified as a non-significant risk.

For MRI, the long-term effects of being placed in a magnet of this strength (3 Tesla) are unknown, but there have been no reports of any long-term ill effects caused by magnets of the same or even higher strength, either here or elsewhere. However, although there are no known risks associated with pregnancy, pregnancy tests will be conducted before each MRI session, and subjects testing positive will be excluded from further participation.

Procedures in Place to Minimize Risk:

Informed Consent:

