De-identified data may also be shared with other investigators at NYSPI for the purposes of substitution in the case of failure of data collection. For instance, if the subject participates in another MRI protocol at NYSPI, and during those sessions the investigators fail to collect all of the needed anatomical and functional MRI sequences, we may share our data with them if we have collected the same types of MRI sequences for our protocol. The inverse may happen as well; we may receive data from another NYSPI protocol if because of a technical failure we are unable to collect all of the necessary MRI sequences.

Direct Benefits to Subjects

Participants may not experience any direct benefits from their involvement in this study.

The proposed project is a clinical trial of TMS for treatment of AVH and an experimental intervention. Therefore, we do not consider AVH treatment a definite benefit of participation. Nevertheless, participants are informed of the purpose of the trial and may in fact experience a reduction in AVH.

MRI findings and clinical assessments are unlikely to be of direct benefit to participants, but subjects will be informed of any clinically significant findings from the MRI and clinical assessments.

Compensation and/or Reimbursement

Subjects will be compensated as follows:

- Pre-treatment session (screening, clinical assessment, EEG and MRI): \$185
- Treatment day: \$100
- Post-treatment session (clinical assessment, EEG and MRI): \$160

In this study, each subject will undergo 1 pre-treatment session, 1 post-treatment session and 10 treatment days. Total compensation for all sessions is \$1345.

Statistical Analysis Plan

We will use a repeated measures t-test to analyze changes in the Auditory Hallucination Rating Scale (AHRS). This involves comparing scores before and after TMS treatment in participants who completed all study procedures. The goal of this analysis is to determine if there are improvements in symptoms of auditory verbal hallucination. Additionally, similar analyses will be performed for secondary outcome measures such as PANSS, investigating if there is a significant decrease in PANSS P3 scores for participants after the TMS treatment sessions.

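### The AHRS test covers only completers and no AHRS is requested after an early stop, so stops prompted by worsening could tilt the estimate modestly toward improvement

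*Combined protocol and SAP*

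**What the plan says.** Under Criteria for Early Discontinuation, a CGI-I worsening of at least 2 on two consecutive days, or a CGI-S of 6 or 7, "will trigger a clinical evaluation as to whether the patient should be discontinued". The same section adds: "Subjects who are unable to cooperate with study procedures (e.g., TMS, EEG, MRI) will be discontinued from the study". Protections Against Risk (item 3) says that patients removed for adverse effects are referred for care, which may include medication or cognitive-behavioural therapy. None of these places mentions a final AHRS.

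The Assessments section fixes the clinical scales at two times: "There will be baseline (week 0) and post-treatment (week 3) assessments". The Procedure Table agrees. During the two treatment weeks only C-SSRS, CGI and SAFTEE are collected. The AHRS is audiotaped for a second reading: "The second clinical rater will listen to an audiotaped session, blind to subject identity and session number".

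The Statistical Analysis Plan describes the paired AHRS test as follows: "This involves comparing scores before and after TMS treatment in participants who completed all study procedures". It gives no all-treated analysis, missing-data method or sensitivity analysis. The rTMS section allows some slack in what counts as a full course: "the treatment will still be considered complete if the participant misses at most two days of treatment".

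**The concern.** The discontinuation rule is a reasonable safety rule. The gap is in the outcome data once the decision is to stop. At least one route out, the CGI-I limb, is defined by clinical worsening. CGI is rated partly on the symptom scales, which include the AHRS, so some link between that worsening and AHRS change is plausible. A patient who leaves by this route has a baseline AHRS and nothing after it, and is also outside the analysis population. With no post-baseline score, a later change of analysis population could not bring that patient back.

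The Lay Summary says that promising reductions in AVH would lay the ground for a sham-controlled trial. With about 10 analysed patients and no control arm, one or two selective losses can move the estimate carried into that decision. Worsening would still appear in CGI, SAFTEE and adverse-event notes, but not in the AHRS change.

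**Working it through.** **Plan figures.** Description of Subject Population gives 10 completers from 12 enrolled, an implied loss of 2/12 = 16.7%. Inflating, 10/(1 − 2/12) = 12, which agrees. The rate is back-derived, so this checks consistency only. The documents state no alpha, SD of change, effect size or power.

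**Who falls outside the test.** CGI is rated before each session, so a stop at pre-session rating *j* leaves *j* − 1 sessions delivered. A complete course needs at least 10 − 2 = 8. Stops at *j* ≤ 8 leave at most 7 and are incomplete. Stops at *j* = 9 or 10 leave 8 or 9 and can still count as complete treatment.

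**Assumptions, not in the documents.** 12 patients start rTMS; AHRS change is normal with true mean 0, in SD units, positive meaning worse; two-sided test at 0.05. The worsening that prompts a stop is *z* = *r* × change + √(1 − *r*²) × noise. The t-test is run on those who remain. The simulations behind the table used 400,000 to 2.5 million trials per row.

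| Who is lost | Mean shift (SD) | False significant improvement |
|---|---|---|
| Two at random | 0.00 | 2.5% |
| *z* above 2, *r* = 0.5 (0.27 lost on average) | −0.027 | 3.0% |
| *z* above 1.5, *r* = 0.5 (0.80 lost) | −0.069 | 4.0% |
| *z* above 1, *r* = 0.5 (1.90 lost) | −0.144 | 6.1% |
| One worst-rated and one at random, *r* = 0.3 / 0.5 | −0.044 / −0.075 | 3.4% / 4.3% |
| Two worst-rated, *r* = 0.3 | −0.082 | 4.4% |
| Two worst-rated, *r* = 0.5 | −0.137 | 6.4% |
| Two worst-rated, *r* = 1 (limit only) | −0.275 | 18.1% |

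The shifts can be checked by hand. For a threshold *c* the shift is −*r* φ(*c*)/Φ(*c*): at *c* = 1.5, 0.5 × 0.1295/0.9332 = 0.069; at *c* = 2, 0.5 × 0.0540/0.9772 = 0.028. For two worst-rated stops the shift scales with *r*: 0.5 × 0.275 = 0.137 and 0.3 × 0.275 = 0.082.

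**Which rows are realistic.** The protocol's risk section puts psychiatric adverse events with rTMS at 1% to 5%. If every such event led to a stop (generous, and assuming the rate applies here), 12 starters give 12 × 0.01 = 0.12 to 12 × 0.05 = 0.6 expected stops. The chance of none is 0.99¹² = 89% to 0.95¹² = 54%; of two or more, 0.6% to 12%. The nearest rows are the 1.5 and 2 SD thresholds, so about 3% to 4% is the better guide.

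**The CGI-S limb.** This is an absolute severity level, not a change. Removing the two most severe, with an assumed pre/post correlation of 0.6, gives 2.5% and no shift if severity relates equally to pre and post AHRS. It gives 1.7% to 3.8% (0.06 SD either way) if it does not.

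**Which score the repaired test should use.** With all 12 analysed and no effect of later care, false improvement returns to 2.5%. Always taking week 3 would count any benefit of rescue care as benefit of rTMS. If rescue improves the two stopped patients by 0.5 or 1 SD, the rate is 4.8% or 7.6% (*r* = 0.3) and 5.3% or 8.9% (*r* = 0.5). The completer test gives 4.4% and 6.4%, so this rule is worse in three of the four cells. The stopping-visit score has the opposite risk: if it is 0.5 SD worse than week 3 would have been, for two of 12, the mean moves 2 × 0.5/12 = 0.08 SD against treatment.

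**The case against.** The CGI rule prompts an evaluation, not an automatic stop, and CGI is a global rating rather than a measure of voices. The protocol's own rates suggest few stops: psychiatric events at 1% to 5%, described as mostly transient and minor, and under 2% leaving because of pain. Twelve starters is a ceiling, since consent precedes screening and the enrolled may include screen failures. An open-label pilot with no stated p-value or effect-size gate may reasonably analyse those who received the planned course, and its intended successor is sham-controlled. All of this stands, and it keeps the size small. It does not remove the gap, because a score not taken at stopping cannot be recovered.

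A reader might infer that every exit reflects worsening voices. The text does not support that. The statement that "subjects will be removed from the protocol if their distress of anxiety becomes intolerable" concerns distress from the assessments themselves. Adverse-effect removals cover any adverse effect, headache and scalp pain included. Exits for non-cooperation may be neutral, as may pregnancy exits, where "subjects testing positive will be excluded from further participation". A reader might also infer that the plan cancels the week-3 visit after a stop. It does not say so; it is silent, and the completer restriction would exclude the score in any case.

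**Conclusion.** The gap is real: the AHRS test is limited to completers, no AHRS is requested after an early stop, and one stopping route is tied to clinical worsening. Any resulting bias would favour improvement, but only to the extent that such stops occur and track AHRS change, and the documents give neither. Under the stated assumptions with *r* = 0.5, false significant improvement is about 3% to 4% for stops above a 1.5 to 2 SD threshold, against 2.5%, and about 6.4% if the two worst-rated are lost. If stopping is unrelated to AHRS change there is no bias.

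The 18.1% figure should not be read as an expected error rate. It requires two stops that are exactly the two largest AHRS deteriorations. Nor do the documents support saying that the pilot's result will be biased; they support saying that it could be, and that the data needed to check would be missing.

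**What to change.** 1. Add to Criteria for Early Discontinuation: *A participant who stops rTMS after at least one session completes the audiotaped AHRS at the stopping visit, before any new treatment where possible, and again at week 3 if willing and clinically able; this is not asked of anyone who withdraws consent or is removed because the assessments cause intolerable distress.* The other scales are optional. The CGI criteria stay as they are.

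2. Amend the SAP so that the main paired AHRS t-test includes every participant with at least one rTMS session and a post-baseline AHRS. Use week 3, unless new medication or therapy was started after stopping or week 3 is missing; then use the stopping visit.

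3. Report two sensitivity analyses: the completer test, and a version using week 3 for everyone who has it. The second is needed because the stopping-visit score may be taken at a transient low point. List each stop with its reason and last CGI.

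The cost is two amended paragraphs and, for about 0 to 2 participants, a short AHRS interview at up to two visits, so at most 4 extra interviews and audiotape ratings. If each were paid at the full $160 post-treatment rate, the ceiling is 4 × $160 = $640. No EEG or MRI is added. The burden falls on patients who may be unwell, which is why the request is limited to the AHRS and carries exemptions. The resulting estimate may be slightly less favourable.

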through the skull, effectively depolarizing neurons up to two centimeters into the brain. The effects are not entirely local, as the depolarized neurons transmit their activity transsynaptically to connected subcortical and transcortical regions within functional networks. The actual neurobiological effects depend on the intensity of the magnetic field, the coil shape and its orientation, and the geometry of the underlying cortex in relation to the field. The neural effects of TMS also depend on the frequency of stimulation when applied repetitively in a pulse train (rTMS). While rTMS is FDA approved for the treatment of depression, it is also proposed as a novel treatment for schizophrenia patients with treatment-resistant AVH when applied using inhibitory frequencies over left language-receptive areas. rTMS is generally well tolerated and safe but see "Risks and inconveniences" section for a detailed discussion of potential adverse effects. Current studies of 1-Hz (inhibitory) rTMS targeting speech perception areas such as left TPJ/Wernicke's area have yielded mixed results in reducing AVH. However, most of these studies use scalp-based targeting approaches that don't account for individual variability in underlying brain anatomy (Briend et al. 2020, Schiz Res.

https://doi.org/10.1016/j.schres.2020.09.001). Here we propose to pilot an individualized MRguided rTMS approach of a left TPJ target to establish feasibility and potential efficacy using an open-label design in ten participants with schizophrenia or schizoaffective disorders with persistent AVH. In addition to assessing pre/post treatment changes in AVH severity and characteristics using established clinical scales, we will also assess pre/post changes in etiologically-relevant fMRI and neurophysiological (EEG) biomarkers.

Specific Aims and Hypotheses

Specific Aim 1: To evaluate the efficacy of individualized MR-guided inhibitory rTMS in reducing AVH symptoms in Sz. We hypothesize that TMS targeting an area of left TPJ involved in receptive language processing will reduce AVH severity.

Specific Aim 2: To evaluate the utility of etiologically relevant MRI tasks and EEG biomarkers in tracking treatment response. We hypothesize that pre/post treatment changes in AVH severity will correlate with normalization of previously established deficits in MRI and EEG measures associated with AVH.

Description of Subject Population

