Population: Adults with schizophrenia and schizoaffective disorder Number of completers required to accomplish study aims: 10 Projected number of subjects who will be enrolled to obtain required number of completers: 12 Age range of subject population: 22-55

Gender, Racial and Ethnic Breakdown

Based on prior studies of schizophrenia at NYSPI/Columbia:

60% male; 40% female 1/3 Hispanic; 2/3 non-Hispanic 50% Caucasian; 30% African-American; 10% Asian-American; 10% Mixed Race or Other We will not exclude any subjects based on gender or ethnicity/race. Females of childbearing potential will be permitted to participate as long as they remain on adequate birth control. The proportions of ethnic groups in our study population reflect the demographics of schizophrenia patients within our catchment areas, and a significant proportion of Hispanic and African-American subjects are included in our studies. Prior trials conducted by our group have consistently obtained a demographic mix that is representative of schizophrenia within the New York City and Rockland County populations, particularly our neighborhood of Washington Heights, which has a large percentage of African American and Hispanic residents.

The demographics of schizophrenia in the United States are $\sim 1\%$ of the population of each ethnicity, with the exception of more men (ratio 1.4:1) and a 2 to 3 fold increased rate in African Americans (Regier et al, Acta Psychiatr Scand 1993, Bresnahan et al, Int. J. Epidemiol, 2007). The literature supports that the demographics of schizophrenia in any specific area, such as New York City in general, and Washington Heights specifically should reflect the demographics of the area (Reiger 1993). For example, Washington Heights (the neighborhood in which the New York State Psychiatric Institute is located) has a large percentage of Hispanic people with schizophrenia because of the relatively large number of Hispanic people in Washington Heights.

Because we will be recruiting **a portion of the participants** from the study (protocol # 7114) within our division, we have used composite demographics from SZ patients in the study (which are representative of schizophrenia patients within the New York City and Rockland County areas) for the breakdown above.

Description of subject population

Subjects will be patients diagnosed with Schizophrenia or Schizoaffective Disorder, who suffer from AVH. Inclusion/exclusion criteria were based on previous studies.

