Suicide Risk Management Plan

The rater who will be conducting C-SSRS has a master's degree in clinical psychology and has many years of experience working with vulnerable clinical patients. The rater has been administering C- SSRS under other protocols for the past two years. The C-SSRS will be conducted every week of the four-week study. In addition, the study PI (MD/PhD) will conduct a rigorous assessment with participants prior to the start of treatment, including asking if they have suicidal thoughts and plans, which will be recorded on the evaluation note form in the redcap. After the screening session, the study PI and the rater will go through the inclusion/exclusion criteria together to determine the patient's eligibility. On each day of the 10-day treatment, a covering MD will ask a series of questions about the patient's symptoms, mood, suicidal thoughts and medication use before starting the session. These will be recorded in the progress note form on the redcap after each day of treatment. All research members involved in the study have completed all necessary CITI training courses to ensure the safety and welfare of participants.

The rater will gather lifetime history of suicidality as well as any recent suicidal ideation and

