5. If female and not infertile, must agree to use one of the following forms of contraception for the duration of study participation: systemic hormonal treatment, an IUD which was implanted at least 2 months prior to screening, or "double-barrier" contraception. Women of child bearing potential must have a negative pregnancy test at screening.	Self-report, urine pregnancy test		
6. Right handed	Edinburgh Handedness Inventory		
7. Normal hearing	Mean audiometry ≤25 dB above age corrected norms		
8. Taking an antipsychotic medication at a stable dose for at least 4 weeks. All oral and depot antipsychotics are allowable.	Self report		

Exclusion

Criterion	Method of Ascertainment
1. Substance use disorder (excluding	SCID and self report

nicotine) within last 90 days, or positive	
toxicology screen for any	
substance of abuse	
2. Pregnancy	Urine pregnancy test at screening
3. Participation in study of	Self report
investigational medication/device	1
within 4 weeks	
4. History of seizure, epilepsy and	Physician evaluation/Medical history/TASS
neurologic conditions with structural	
cerebral damage, including stroke,	
multiple sclerosis, traumatic brain	
injury, Alzheimer's and other	
neurodegenerative diseases,	
meningoencephalitis or intracerebral	
abscess, parenchymal or	
leptomeningeal cancers, dementia,	
developmental disability,	
cerebrovascular disease, increased	
intracranial pressure, or central	
nervous system (CNS) tumors, brain	
surgery, head injury with loss of	
consciousness >1 hour or clear	
cognitive sequelae, intracranial metal	
implants, known structural brain	
lesion	
5. Subjects with devices that may be	Physician evaluation/Medical history/TASS
affected by TMS (pacemaker,	
cardioverter defibrillator, medication	
pump, intracardiac line, cochlear	
implant, implanted brain	
stimulator/neurostimulator)	
6. Subjects with suicidal ideation with	Columbia Suicide Severity Rating Scale
intent or plan (indicated by	(CSSRS)
affirmative answers to items 4 or 5 of	
the Suicidal Ideation section of the	
baseline C-SSRS) in the 6 months	
prior to screening or subjects who	
represent a significant risk of suicide	
in the opinion of the investigator	
7. Frequent and persistent migraines	Physician evaluation/Medical history
8. Clinically significant skin disease	Physician evaluation/Medical history
9. Presence of unstable medical	Physician exam with vital signs/Medical
disorders, including those that are previously	history

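### Does the lack of a date limit on substituted MRI scans undermine the pre/post fMRI analysis?

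*Combined protocol and SAP*

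**What the plan says.** The substitution clause stands in the data-sharing paragraph of Methods to Protect Confidentiality. It first describes lending data to other NYSPI investigators who "fail to collect all of the needed anatomical and functional MRI sequences", subject to the condition "if we have collected the same types of MRI sequences for our protocol". It then allows the reverse: "we may receive data from another NYSPI protocol if because of a technical failure we are unable to collect all of the necessary MRI sequences". No acquisition window, timepoint or medication condition is attached, and the Statistical Analysis Plan has no rule for a substituted scan.

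Four other places bear on the point.

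- **Timing.** Study Procedures puts the trial's own MRI at week 0 and week 3. For the clinical scales, Assessments says: "There will be baseline (week 0) and post-treatment (week 3) assessments".
- **Medication.** Inclusion criterion 8 reads "Taking an antipsychotic medication at a stable dose for at least 4 weeks". During treatment, a physician asks each day about "symptoms, mood, suicidal thoughts and medication use before starting the session" (Suicide Risk Management Plan).
- **Use of the scans.** Aim 2 predicts that "pre/post treatment changes in AVH severity will correlate with normalization of previously established deficits in MRI and EEG measures associated with AVH". For fMRI, the Statistical Analysis Plan says only that functional connectivity will be evaluated.
- **Possible donor.** Protocol #7114 supplies "a portion of the participants" (Description of Subject Population). Study Procedures describes it as cross-sectional with 2 hours of MRI. It gives neither the sequences nor the time between that scan and entry to this trial.

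**The concern.** Aim 2 compares two changes in the same patient, and the comparison is cleanest when both cover the same weeks. A baseline scan borrowed from an earlier study would stretch that patient's fMRI interval backwards and leave the AHRS interval at week 0 to week 3. The entry rule assures a stable antipsychotic dose only for the 4 weeks before entry, and the daily medication question starts with treatment. An earlier dose change, or ordinary drift, could therefore enter that patient's fMRI change and not the AHRS change. The trial is open-label with no control arm, so no comparison group would reveal it. With only 10 completers, one odd pair might seem able to distort the result.

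The reading that functional scans are covered is reasonable but inferred. The sentence on incoming data speaks only of necessary sequences, and the word functional comes from the lending case that it inverts. A structural scan used to position the coil is not at issue.

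**Working it through.** The plan states no figure on this point, so there is none to reproduce. The check has four parts.

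**1. What the dosing rule says about a scan.** Criterion 8 is a minimum for admitting a participant and sets no date for any scan, so a scan cannot breach it. Take the 4 weeks as counted back from week 0, and assume scan ages, since none are given. The pre/post interval is scan age + 3 weeks.

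| Scan age before week 0 (weeks) | Pre/post interval (weeks) | Weeks beyond assured stable dosing |
|---|---|---|
| 0 | 3 | 0 |
| 4 | 7 | 0 |
| 8 | 11 | 4 |
| 26 | 29 | 22 |
| 52 | 55 | 48 |

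A scan more than 4 weeks old is only not assured to fall in a stable period. The dose may have been stable for far longer than the minimum.

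**2. Effect on the mean fMRI change.** A shift of d SD in one of n = 10 patients moves the mean by d/n: 0.5/10 = 0.05, 1/10 = 0.10 and 2/10 = 0.20 SD. The 95% half-width is t(0.975, n−1)/√n:

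- n = 10: 2.262/√10 = 0.72 SD
- n = 9 (patient left out): 2.306/√9 = 0.77 SD

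**3. Effect on a correlation between fMRI change and AHRS change.** Aim 2 implies this test, but the Statistical Analysis Plan does not specify it. The smallest |r| reaching two-sided p<0.05 is t/√(t² + n − 2):

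- n = 10: 2.306/√(5.318 + 8) = 0.632
- n = 9: 2.365/√(5.592 + 7) = 0.666

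Power was simulated with 300,000 trials of 10 patients. The two changes were bivariate normal with unit SD. Independent normal drift of SD s was added to one patient's fMRI change. Both the true r and s are assumptions.

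| Case | True r = 0.7 | True r = 0.5 |
|---|---|---|
| No failure | 68% | 33% |
| Older baseline, s = 0.5 | 66% | 32% |
| Older baseline, s = 1 | 62% | 30% |
| Older baseline, s = 2 | 52% | 26% |
| Patient left out (n = 9) | 62% | 29% |

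Keeping the scan matches leaving the patient out at about s = 1 when r = 0.7, and at about s = 1.25 when r = 0.5. Below that, substitution is the better choice. Above it, omission is.

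**4. False positives.** With no true association, the same model gives 5.0% significant correlations at s = 1 or 2. With no true mean change, the paired t-test rejects in 4.5% to 4.9% of trials, whether the one patient's shift is random with SD 1 or 2 or fixed at 1 or 2 SD. A fixed shift in one patient raises the variance along with the mean, so the test does not become liberal.

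**The case for a change.** The strongest case for a change is that it would be cheap and would settle the matter before the data are seen. A sentence or two could require a matching sequence and task, record the scan date and any antipsychotic change, and show the fMRI result with and without the substitute. That would prevent a choice between keeping and dropping a scan being made after seeing which looks better, which is a fair worry with 10 patients. An earlier scan may well exist, because #7114 is a recruitment source and includes MRI.

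Much of this stands. The clause has no date limit, the Statistical Analysis Plan is silent, and reporting the date of a borrowed scan is good practice. It does not amount to a fault in the plan, for three reasons.

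- The measure is pre/post throughout, and a scan from a cross-sectional recruitment source would ordinarily precede treatment. The sensible use is therefore as a baseline, and nothing directs an untreated scan into the post-treatment slot.
- Reporting the date would not separate drift from a stimulation effect. Without a control arm, that separation is unavailable for every pair in the trial, borrowed or not.
- The additions would be records and a sensitivity run. A fixed rule to keep or to omit the scan is not shown to do better, since which is preferable depends on drift that the documents do not give.

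**Conclusion.** No change is needed. The gap is a missing detail in a permission, of a kind that analysts fill sensibly by using the scan as a baseline, checking that it matches, and stating its date when reporting.

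For harm to arise, several things must coincide: a technical failure, the same patient scanned under another NYSPI protocol, a matching functional sequence, a scan older than the assured 4 weeks, a real dose change or drift, and use of that scan in a change score. The documents give no rate for any of these, and do not show that #7114 holds a matching functional scan.

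If it did happen once, the likely result is a modest loss of precision in the exploratory fMRI part of Aim 2: at most 0.20 SD on the mean for drift up to 2 SD, and power between 52% and 66% instead of 68% at an assumed r of 0.7. Type I error is not inflated. These sizes rest on assumed drift, assumed correlations, normal data and a single substitution; several substitutions would cost more. The AHRS and other clinical scores do not use these scans. Whether a participant with a failed scan still belongs in the AHRS completer analysis is a separate question that the age of a donor scan does not affect.
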